## Hypotheses

Primary outcome: We hypothesize that graphic health warnings will be perceived as most stigmatizing, followed respectively by text-only health warnings, nutrient warnings, and control labels (H1). We also hypothesize that, for all label types, the modified version will be perceived as less stigmatizing than the regular version of the same label (H2).

Secondary outcomes: We hypothesize that graphic health warnings will be perceived as most effective, followed respectively by text-only health warnings, nutrient warnings, and control labels (H3). We also hypothesize that graphic health warnings will elicit the most weight bias, followed respectively by text-only health warnings, nutrient warnings, and control labels (H4).

## Main Analyses

We will use a two-sided critical alpha of 0.05 to conduct all statistical tests. All confidence intervals presented will use a 95% confidence level. Analyses of the primary and secondary outcomes will include all participants according to the trial arm to which they were randomized. We will use complete case analysis to handle any missing data.

To prepare the data, we will verify that Cronbach's alpha for all scales is sufficient ( $\geq 0.7$ ) and, if so, we will average items to create a mean score on each scale for each

participant. If Cronbach's alpha is not sufficient (<0.7), we will drop items as necessary to improve reliability or treat items as separate constructs.

We will first descriptively report unadjusted means for the primary and secondary outcomes for each experimental arm. To test H1 and H2 (model 1) and H3 (model 2), we will fit separate mixed-effects models with random intercepts to account for repeated measures within participants. These models will include indicator variables for label type (i.e., nutrients, text-only, and graphic - the control label type will be omitted as the referent group), an indicator variable for label version (i.e., regular vs. modified), and interaction terms between label type and label version (i.e., nutrients\*modified, text-only\*modified, and graphic\*modified). To test H4 (model 3), we will fit a linear model including only indicators for label type.

If the interaction terms in models 1 and 2 are not significant, after fitting models 1-3, we will use these models to estimate the main average differential effects of label types (i.e., differences in predicted means between label types averaging between the two version of each label). We will obtain the effect of each label type vs. control, as well as of nutrient vs. text-only, text-only vs. graphic, and nutrient vs. graphic label types. If, in turn, the interaction terms in models 1 and 2 are significant, after fitting models 1 and 2, we will estimate the average differential effects of label types and report them separately for each version of the labels (i.e., we will present differences by label type separately for regular labels and for modified labels). We will not adjust the p-value for each label type compared to control, but will adjust for multiple tests for the three additional pairwise comparisons using the Bonferroni-Holm correction.

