## Study Protocol

Participants will complete an online randomized experiment programmed in Qualtrics. After providing informed consent and completing an initial parent experiment on alcohol messages, participants will be randomly assigned to view 1 of 4 types of front-of-package labels for sugar-sweetened beverages: neutral control labels, nutrient warning labels, text-only health warning labels, or graphic warning labels. In random order, they will view and rate two versions of their assigned label type on perceived weight stigmatization (primary outcome) and perceived message effectiveness (secondary outcome). The two versions will differ only on whether their content references calories or obesity (i.e., the modified version will not reference either). After rating each version of the label, participants will complete measures of weight bias (secondary outcome) and demographic characteristics.

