## **Sample Size and Power**

This study will occur in a survey that will follow a parent experiment about alcohol messages. The total sample size (~2,500 participants) was calculated based on the primary outcomes of the parent experiment.

Using G\*Power3.1 and specifying a between-within subjects ANOVA (which should most closely approximate the proposed mixed linear model), we determined the

minimum effect size we would be able to detect on our primary outcome with this pre-determined sample size. With 80% power, a critical alpha of 0.05, four conditions, and two repeated measures, we would be able to detect an effect of  $f=0.057$  (equivalent to  $d=0.11$ ) or larger for the between-subjects factor, and  $f=0.028$  (equivalent to  $d=0.06$ ) or larger for the within-subjects factor. Given that a previous study to analyze the effect of FOPLs on perceived weight stigmatization obtained an effect size of  $d=0.25$  comparing nutrient warnings to control, this study's sample should be sufficiently large to detect an even smaller effect when comparing between nutrient warnings and text-only health warnings, which we expect to be the smallest effect.

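### Does H2 go untested because the plan lists only contrasts between label types?

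*Combined protocol and SAP*

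**What the plan says.** Study Protocol randomizes each participant to one of four label types: "neutral control labels, nutrient warning labels, text-only health warning labels, or graphic warning labels". Everyone rates two versions of the assigned type, so type varies between people and version within them.

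Hypotheses gives H2, on the primary outcome, as: "for all label types, the modified version will be perceived as less stigmatizing than the regular version of the same label".

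Main Analyses names model 1 as the test of both H1 and H2. It is a random-intercept mixed model with three type indicators ("the control label type will be omitted as the referent group"), "an indicator variable for label version (i.e., regular vs. modified", and three type-by-version interactions. The general rule for inference is: "We will use a two-sided critical alpha of 0.05 to conduct all statistical tests". Intervals are at 95%.

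The estimates to be drawn from the model are then described. If the interactions are not significant, they are "differences in predicted means between label types averaging between the two version of each label". If they are significant, "we will present differences by label type separately for regular labels and for modified labels". The six listed pairwise comparisons and the Holm step all concern label types.

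Sample Size and Power reports a detectable effect of f = 0.028 (d = 0.06) "or larger for the within-subjects factor".

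**The concern.** H2 is about version within type, but both post-estimation branches are about type. Nothing names a modified-versus-regular difference, pooled or per type, or says what pattern of results would support H2.

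Reading the coefficient table does not settle it. With control as referent and the interactions retained, the version coefficient is the difference in the control arm, and each interaction is only a departure from that difference. An analyst who took the version coefficient as the H2 result would be reporting on the neutral labels alone.

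If the gap were real, the choice among an averaged effect, four separate effects, or a requirement that all four be significant could be made after seeing the data, on a primary hypothesis. These readings have very different power when the version effect is small.

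**Working it through.** **1. Can model 1 deliver H2?** Write V for the version coefficient (modified minus regular) and I(N), I(T), I(G) for the nutrient, text-only and graphic interactions. The within-type differences are:

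- control: V
- nutrient: V + I(N)
- text-only: V + I(T)
- graphic: V + I(G)
- average over types: V + [I(N) + I(T) + I(G)]/4

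Every term is already in the model, so no new model, data or assumption is needed.

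**2. Reproduce the plan's figures.** Inputs from Sample Size and Power: N about 2,500, four conditions, two measures, 80% power, alpha 0.05. The plan states no within-person correlation r; 0.5 is assumed.

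- Within-person factor: noncentrality = f² × N × 2/(1 − r) = 0.028² × 2,500 × 2/0.5 = 7.84 on 1 and 2,496 df. Power is 79.9%.
- Between-person factor: noncentrality = f² × N × 2/(1 + r) = 0.057² × 2,500 × 2/1.5 = 10.83 on 3 and 2,496 df. Power is 79.6%.

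Both figures reproduce. With two levels, d = 2f = 0.056, which rounds to the stated 0.06. It is the version effect pooled over all participants, which is what the plan attaches it to.

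**3. One label type.** Assume equal allocation, 2,500/4 = 625 per arm. Detectable d = (1.960 + 0.842) × √[2(1 − r)/n].

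- Pooled, n = 2,500, r = 0.5: 2.802 × 0.02 = 0.056
- One type, n = 625, r = 0.5: 2.802 × 0.04 = 0.112
- One type, r = 0.3 and 0.8: 0.133 and 0.071
- 80% power that all four are significant needs 0.8^(1/4) = 0.946 per type, so d of about 0.143 (0.169 at r = 0.3, 0.090 at r = 0.8)

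**4. How far the readings differ.** Same version effect in every type, r = 0.5, unadjusted. The all-four figure is the fourth power of the one-type figure, since the four contrasts come from separate arms.

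| d | Averaged | One type | All four |
|---|---|---|---|
| 0.06 | 85% | 32% | 1% |
| 0.10 | >99% | 71% | 25% |
| 0.143 | >99% | 95% | 80% |
| 0.20 | >99% | >99% | >99% |

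For r from 0.3 to 0.8, all-four power runs from 10% to 91% at d = 0.10 and from 95% to above 99% at d = 0.20.

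**5. A case with unequal effects.** Suppose control has no version effect and each warning type has d = 0.10 (r = 0.5).

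- The version coefficient is significant 5% of the time.
- The averaged effect is (0 + 3 × 0.10)/4 = 0.075, with power 96%.
- All four are significant in the hypothesised direction with probability 0.025 × 0.705³ = 0.009.

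This is not lost power. With no effect in control, H2 as worded is false. The 5% is a nominal error rate, the 0.9% is correct non-support, and the 96% would be the misleading answer if it were taken as support for every type.

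**6. Multiplicity.** If no type has an effect, the chance of at least one two-sided rejection in four unadjusted tests is 1 − 0.95⁴ = 18.5%. In the hypothesised direction it is 1 − 0.975⁴ = 9.6%. Requiring all four needs no adjustment.

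**The case for a change.** The best argument for a change is that the document exists to fix the analysis before data collection, and H2 is primary. Step 4 shows that the averaged and all-four readings can reach opposite conclusions for small effects. The plan gives no expected version effect: the d = 0.25 in Sample Size and Power compares nutrient warnings with control, so it cannot show that the choice is harmless. Nor would the interaction step reliably flag unequal effects. In the case in step 5, a joint 3-df test, which the plan does not specify, has power of only about 41%.

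All of this is accurate, and the modified-versus-regular contrast is indeed implicit. It does not show that H2 goes untested or that the wrong quantity will be used. The plan says model 1 tests H2. It nowhere makes the version coefficient the test; where it describes estimates it uses differences in predicted means, averaged or split according to the interaction. Carried over to version, that logic gives the averaged difference or the four within-type differences.

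The hypothesis itself says which label types are meant. H1, H3 and H4 have no explicit support rule either, and once four differences with intervals are reported a reader can apply any rule. Leaving them unadjusted would match the plan's stated treatment of the comparisons with control.

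**Conclusion.** No change is called for. This is a gap in wording that a competent analyst fills from the plan itself: model 1 contains all the terms, and alpha, sidedness and intervals are set. Writing the contrast down would correct no number or rule, and whether to announce H2 as supported overall or to report four estimates is a matter of presentation.

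What remains is a caution in reading the results. The version coefficient describes control only, and the sensitivity for a single label type is about d = 0.11 (0.13 to 0.07 for correlations of 0.3 to 0.8), not 0.06. The readings of H2 diverge mainly when the version effect is below roughly d = 0.14 at a correlation of 0.5, or when it differs between types.

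These figures rest on 625 per arm and on the assumed correlation, of which 0.5 is the value that reproduces the plan's own detectable effects. The table also assumes the same version effect in every type.

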## **Exploratory Analyses**

We will examine whether participant characteristics (i.e., gender, age, race/ethnicity, and perceived weight status) moderate the effect of label type (compared to control) on the primary outcome. If the main analysis (model 1) reveals that there is no significant interaction by label type and label version, we will fit a series of mixed-effects models with random intercepts (one for each potential moderator) including label type, label version, the moderator, two-way interactions between label type and label version, and two-way interactions between label type and the moderator. If, in turn, the main analysis (model 1) reveals a significant interaction by label type and label version, we will run separate moderation models for regular labels and for modified labels. We will consider moderation to be supported if the interaction terms between label types and the moderator (in either scenario) are statistically significant, and we will probe such significant interactions by calculating the marginal effect of label types on the outcome at different levels of the moderating variables. We will use Wald tests for categorical moderators with more than 2 categories.

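### Models 1 to 3 omit age, gender and race/ethnicity: the analysis is valid, but prespecified adjustment could make the label-type contrasts modestly more precise, by an unknown amount

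*Combined protocol and SAP*

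**What the plan says.** - **Models 1 and 2** (Main Analyses; perceived stigmatization and perceived effectiveness): "These models will include indicator variables for label type", plus label version, the type-by-version interactions and a random intercept. No participant characteristic enters.
- **Model 3** (Main Analyses; weight bias): "we will fit a linear model including only indicators for label type".
- **Exploratory Analyses:** "gender, age, race/ethnicity, and perceived weight status" are used as moderators, one per model, for the primary outcome only.
- **Study Protocol:** demographics are asked after the label ratings, at the end of the survey.
- **Main Analyses:** missing data are handled by complete-case analysis. Comparisons with control are not adjusted for multiplicity; the three comparisons among warning types are Holm-adjusted.
- **Sample Size and Power:** "The total sample size (~2,500 participants) was calculated based on the primary outcomes of the parent experiment". Nutrient versus text-only is expected to be the smallest effect.

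No section gives a reason for leaving the main models unadjusted, or any figure for how well demographics predict the outcomes.

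**The concern.** Each participant sees one label type, so the contrasts behind H1, H3 and H4 carry the full between-person variance. Covariates that predict the outcome remove part of that variance. The sample size was fixed by another experiment, so adjustment is one of the few ways left to gain precision, and the plan already intends to use these variables.

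Asking demographics after exposure does not disqualify these three, because seeing a beverage label cannot change a person's age, gender or race/ethnicity. Perceived weight status is different: it is self-rated after exposure and could respond to the label.

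What is at stake is some precision, chiefly for nutrient versus text-only, which the plan expects to be smallest and which falls in the Holm family. The d=0.25 cited in Sample Size and Power comes from "comparing nutrient warnings to control", a different contrast, so it does not show how much power is spare for that one.

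**Working it through.** **Inputs from the documents.** N about 2,500; four label types ("participants will be randomly assigned to view 1 of 4 types of front-of-package labels for sugar-sweetened beverages"); "With 80% power, a critical alpha of 0.05, four conditions, and two repeated measures"; two-sided tests ("We will use a two-sided critical alpha of 0.05 to conduct all statistical tests").

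**Assumptions.** Equal allocation (2,500/4 = 625 per label type; no ratio is stated). Correlation between the two ratings rho = 0.5 (not stated; supported by step 1). R-squared (R2), the share of one rating's variance explained by the three covariates, runs from 0% to 10%. Effects d are in units of the SD of a single rating.

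**1. Reproduce the plan's figures.** These use the noncentral F for a between-within ANOVA with k = 4 groups and m = 2 measures.
- Between: lambda = N f² m/(1 + (m − 1)rho) = 2,500 × 0.057² × 2/1.5 = 10.83 on 3 and 2,496 df; power 79.6%.
- Within: lambda = N f² m/(1 − rho) = 2,500 × 0.028² × 2/0.5 = 7.84 on 1 and 2,496 df; power 79.9%.

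Both stated values (f=0.057 and f=0.028) reproduce at rho = 0.5. They do not at rho = 0, 0.3 or 0.7, where the between-subjects f would be 0.047, 0.053 or 0.061.

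**2. Effect of adjustment on the standard error.**
- Version-averaged contrast: the person mean has variance (1 + rho)/2 = 0.75 of a single rating. A participant-level covariate acting equally on both ratings therefore explains R2/0.75 of it, and SE ratio = sqrt(1 − R2/0.75).
- Single score (weight bias, or a version-specific contrast): SE ratio = sqrt(1 − R2).
- Equivalent extra participants: 2,500/(SE ratio)² − 2,500.

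| R2 of one rating | SE fall, version-averaged | Equivalent extra N | SE fall, single score | Equivalent extra N |
|---|---|---|---|---|
| 0% | 0% | 0 | 0% | 0 |
| 1% | 0.7% | 34 | 0.5% | 25 |
| 2% | 1.3% | 68 | 1.0% | 51 |
| 5% | 3.4% | 179 | 2.5% | 132 |
| 10% | 6.9% | 385 | 5.1% | 278 |

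Example at R2 = 5%: 0.05/0.75 = 0.0667; sqrt(0.9333) = 0.966; 2,500/0.9333 − 2,500 = 179.

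**3. What this means for pairwise comparisons.** Minimum detectable d at 80% power and alpha 0.05 is (1.960 + 0.842) × SD × sqrt(2/625). Version-averaged, SD = sqrt(0.75), which gives 0.137 unadjusted. For one score it gives 0.158. The other columns use R2 = 2%, 5% and 10%.

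| Quantity | Unadjusted | 2% | 5% | 10% |
|---|---|---|---|---|
| Minimum detectable d, version-averaged | 0.137 | 0.135 | 0.133 | 0.128 |
| Power at d=0.10, version-averaged, alpha 0.05 | 53.2% | 54.3% | 56.1% | 59.2% |
| Power at d=0.15, version-averaged, first Holm step (0.05/3) | 74.8% | 76.1% | 78.1% | 81.5% |
| Power at d=0.15, single score, alpha 0.05 | 75.5% | 76.4% | 77.7% | 79.8% |

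At d=0.25, version-averaged power at alpha 0.05 is already 99.9% unadjusted.

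**4. Costs.**
- About 10 extra parameters: sqrt(2,495/2,485) = 1.002, or 0.2% on the SE.
- If the complete-case rule also covered covariates, SE ratio = sqrt((1 − R2)/(1 − share lost)) for one score. With R2 = 2% and 5% lost, sqrt(0.98/0.95) = 1.016, which is worse than not adjusting. Break-even comes when the share lost equals R2 (R2/0.75 for version-averaged contrasts).

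**5. H2.** Regular versus modified is a within-person difference. A participant-level main effect cancels from it, so precision is essentially unchanged.

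**The case against.** The strongest reply is that nothing here is wrong. Label type is randomised, the unadjusted contrasts are valid, and adjusted versus unadjusted is largely a design preference. That stands. A reader might infer from the missing covariates that the estimates are biased or the trial underpowered; the documents support neither. Randomisation protects the contrasts, and power at the plan's reference effect exceeds 99%.

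Second, the gain depends on a figure the documents do not supply. No section says demographics predict any of the outcomes, so the gain may be nil. This stands, and the range above starts at zero for that reason.

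Third, a reader might think adjustment is free and cannot introduce bias. The documents do not support that either. Demographics come last, under a complete-case rule, so adding covariates with no other change would drop participants whose outcomes were observed. A missing category prevents the loss, but a label that cannot alter someone's age could still alter whether they answer at the end. The missingness indicator is therefore a post-randomisation variable. No missingness rate is given, so this is a caveat and not a demonstrated harm.

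Fourth, the larger gains apply only when effects are averaged over versions. If the interactions are significant, the plan reports label-type differences by version, and the single-score figures apply.

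On the other side, the reference d=0.25 belongs to nutrient versus control. At d=0.15 and the first Holm step, unadjusted power is about 75%, so some extra precision is useful. A contrast as small as d=0.10 would stay weakly powered either way.

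**Conclusion.** The point holds as a low-cost efficiency improvement of unknown size. The plan leaves possible precision unused in the label-type contrasts for H1, H3 and H4: from nothing up to about a 7% smaller standard error when averaging over versions, and up to about 5% for weight bias or version-specific contrasts, over an assumed R-squared of 0% to 10%. H2 is not affected. The figures rest on equal allocation, a between-rating correlation of 0.5 (consistent with the plan's own power figures), covariate effects common to both versions, and no loss of participants through missing covariates. The unadjusted analysis is sound as it stands.

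**What to change.** In Main Analyses, before data collection:

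1. Add age (continuous), gender and race/ethnicity as prespecified main effects in models 1, 2 and 3.
2. Leave out perceived weight status, because it is self-rated after exposure.
3. Exempt these covariates from the complete-case rule: a missing category for gender and race/ethnicity, and mean plus a missing indicator for age. No participant with observed outcomes is then dropped.
4. Report covariate missingness by arm.
5. Report the unadjusted models as a sensitivity analysis.

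The cost is SAP wording and a few model terms, with no new data; the extra parameters add about 0.2% to the SE. The remaining downside is that missingness could differ by arm because demographics are asked last. Items 4 and 5 would reveal this.

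### Bonferroni-Holm is valid for the three warning-type contrasts, but Shaffer's step-down keeps the same 5% bound and every Holm rejection, with modestly more power when the steps are small

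*Combined protocol and SAP*

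**What the plan says.** Main Analyses sets the error rate for every test: "We will use a two-sided critical alpha of 0.05 to conduct all statistical tests". After the models are fitted, each label type is compared with control, "as well as of nutrient vs. text-only, text-only vs. graphic, and nutrient vs. graphic label types". The comparisons with control stand outside any correction ("We will not adjust the p-value for each label type compared to control"). For the other three, the plan "will adjust for multiple tests for the three additional pairwise comparisons using the Bonferroni-Holm correction". If label type and version interact in models 1 and 2, these differences are reported separately for regular and modified labels.

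The contrasts serve ordered hypotheses. H1 states that "graphic health warnings will be perceived as most stigmatizing, followed respectively by text-only health warnings, nutrient warnings, and control labels"; H3 and H4 predict the same order for perceived effectiveness and weight bias. Sample Size and Power says the sample should be large enough "when comparing between nutrient warnings and text-only health warnings, which we expect to be the smallest effect". The sample was not sized for this study: "The total sample size (~2,500 participants) was calculated based on the primary outcomes of the parent experiment". The plan gives no reason for choosing Holm and no power for the corrected contrasts.

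**The concern.** Holm works for any three hypotheses, however related. After the first rejection it tests the next contrast at 0.025, to allow for two true nulls remaining. With all pairs of three means that cannot happen once one pair truly differs: if nutrient and graphic differ, text-only cannot equal both. The plan could therefore use a less strict second step with the same guaranteed 5% bound.

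Two of the three adjacent steps in the H1, H3 and H4 orderings lie in this family, and one of them is the contrast the plan expects to be smallest. Since the parent experiment fixed the sample size, the choice of test is one of the few ways left to gain power for these contrasts.

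**Working it through.** **Inputs.** From the documents: two-sided 0.05, four arms, two ratings per participant, about 2,500 participants, 80% power. Assumed, because not stated: equal allocation (2,500/4 = 625 per arm), complete data, and the step sizes between warning types. The within-person correlation ρ is not stated either; 0.5 is inferred next.

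**The plan's own figures.** For the repeated-measures ANOVA with N = 2,500 and m = 2:
- Between: λ = f²·N·m/(1+(m−1)ρ), df 3 and 2,496. With ρ = 0.5 and f = 0.057, λ = 0.003249 × 5,000/1.5 = 10.83 and power is 79.6%. Exactly 80% needs f = 0.0572.
- Within: λ = f²·N·m/(1−ρ), df 1 and 2,496. With f = 0.028, λ = 0.000784 × 5,000/0.5 = 7.84 and power is 79.9%.

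The stated f = 0.057 and f = 0.028 are reproduced at ρ = 0.5, but not at 0 or 0.8. They describe omnibus factor tests, not the corrected contrasts.

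**Error control.** Compare thresholds for the ordered p-values:
- Holm: 0.0167, 0.025, 0.05
- Shaffer: 0.0167, 0.05, 0.05

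The number of true nulls among the three can be:
- three: an error requires the smallest p to be at or below 0.05/3, so by Bonferroni the chance is at most 5%;
- two: impossible, because two equalities imply the third;
- one: an error requires that one p to be at or below 0.05, so the chance is at most 5%;
- none: no error is possible.

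Shaffer therefore holds 5%. Its thresholds are never stricter than Holm's, so it rejects whatever Holm rejects.

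Simulated family error:

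| Truth | Holm | Shaffer |
|---|---|---|
| All three equal | 4.4% | 4.4% |
| One mean 0.14 SD apart (version-averaged) | 3.3% | 4.9% |
| One mean far apart | 5.0% | 5.0% |

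**Power.** Arm means were simulated (400,000 to 600,000 draws per set of runs) with variance 1/625 for one version. For the version average the variance is 0.75/625, since (1+0.5)/2 = 0.75. Steps are in SDs of a single rating.

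Power per adjacent contrast, equal steps:

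| Step | Scale | Holm | Shaffer | Gain (points) |
|---|---|---|---|---|
| 0.10 | averaged | 46.5% | 52.9% | 6.4 |
| 0.10 | one version | 34.0% | 41.5% | 7.5 |
| 0.11 | averaged | 56.1% | 61.2% | 5.1 |
| 0.11 | one version | 42.0% | 49.0% | 7.0 |
| 0.16 | averaged | – | – | about 0.2 |
| 0.16 | one version | 79.6% | 80.8% | 1.2 |

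Check by formula: with no correction, a 0.11 SD contrast on one version has z = 0.11 × √(625/2) = 1.94, so power is Φ(1.94 − 1.96), about 49%. Shaffer recovers nearly all of that.

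Nutrient vs text-only fixed at 0.10 SD, with a larger text-only vs graphic step:

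| Text-only vs graphic | Averaged, Holm → Shaffer | One version, Holm → Shaffer |
|---|---|---|
| 0.15 | 51.2% → 53.2% | 38.3% → 42.3% |
| 0.20 | 52.9% → 53.1% | 41.2% → 42.3% |
| 0.25 | 53.1% → 53.2% | 42.3% → 42.4% |

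Over a grid of unequal steps, the largest gain for any adjacent contrast was about 8 points (one version; steps of 0.08 and 0.12 SD, for the larger step).

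Power to show both adjacent steps, equal steps of 0.10 SD: 18.6% → 20.0% averaged and 8.8% → 10.0% within one version. The largest joint gain found was about 1.4 points.

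**The case against.** The strongest reply is that Holm is a valid, pre-specified procedure, so the point is one of preference. That stands in part: nothing in the plan is contradicted and no conclusion would become invalid. What remains is that another procedure gives the same guaranteed bound and can only add rejections.

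Four stronger readings are tempting, and the documents do not support them.

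- **That Holm's stricter second step is pure waste.** It gives lower realised error in some configurations (3.3% against 4.9% above). Shaffer's extra power comes from using that margin. Both stay within 5%.
- **That the contrast expected to be smallest has most to gain.** If nutrient vs text-only is clearly the smallest effect, the other two contrasts are usually rejected first and Holm then tests it at 0.05 anyway. The gain shrinks to 2 points or less averaged once text-only vs graphic reaches 0.15 SD. It returns (12.3% to 16.9% averaged) when the steps are about 0.05 and 0.10 SD, where power is poor either way.
- **That H1 as a whole gains about 7 points.** H1 is an ordering and needs both adjacent steps, where the gain is about 1.4 points. Its third step, nutrient vs control, is not corrected at all.
- **That a 2-df joint test followed by each pair at 0.05 would serve equally well.** It also controls family error for three groups, but it can miss a Holm rejection. With nutrient vs graphic at z = 2.42 (p = 0.0155) and text-only exactly midway, Holm rejects. The joint chi-square is 2.42² = 5.86 (p = 0.053), so the gate stays shut.

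**Conclusion.** The point holds as an optional efficiency gain, not as an error. Shaffer's step-down keeps family error at or below 5% and keeps every Holm rejection; both follow from the logic of three means and need no assumption about effect size. The size of the benefit does depend on assumptions: equal allocation, complete data, correlation 0.5, and step sizes that the plan does not give. Under these it is worth about 5 to 7.5 points per adjacent contrast when both steps are near 0.10 to 0.11 SD. It is small or nil when either the steps are equal at 0.16 SD or more, or text-only vs graphic is clearly the larger step and nutrient vs text-only is the contrast of interest. For the full ordering it is about 1.4 points. A reader should not infer that the planned analysis is invalid or that the change would rescue a weak test of H1.

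**What to change.** In Main Analyses, replace the Bonferroni-Holm correction by Shaffer's step-down for all pairs of three groups. Apply it within each set of three warning-type contrasts, and within each label version if the interaction branch applies. The rule can be written in full: reject the contrast with the smallest p if it is at or below 0.0167; if it is rejected, test each of the other two at 0.05; otherwise reject none. Adjusted p-values need no special software: three times the smallest p (capped at 1), and for each other contrast the larger of its own p and that value.

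The cost is one clause of SAP wording, plus realised family error nearer to 5% in some configurations. The Introduction says the plan precedes data collection, so the change belongs in the plan before any contrast is seen. Keeping Holm is also defensible; a sentence saying it was chosen for its lower realised error would close the point.
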